5.1. Summary of Study Design

Study IIF-MC-RHCR (RHCR) is a Phase 3b/4, multicenter, randomized, double-blind, parallel-group study evaluating the efficacy and safety of ixekizumab versus guselkumab in patients with moderate-to-severe plaque psoriasis during a 24-week treatment period.

The following treatment groups will be assessed in this study:

- Ixekizumab: 80-mg subcutaneous (SC) injection. At Week 0, a 160-mg starting dose (two 80-mg injections), followed by 80 mg every 2 weeks (Q2W) from Weeks 2 through 12, and then followed by 80 mg every 4 weeks (Q4W), thereafter (i.e., at Weeks 16 and 20).
- Guselkumab: 100-mg SC injection. At Weeks 0 and 4, a 100 mg injection, followed by 100 mg every 8 weeks (Q8W), thereafter (i.e., at Weeks 12 and 20).

[figure not shown]
The study will consist of 4 periods:

- **Period 1: Screening Period** (Visits 1) will assess patient eligibility, occurring approximately 5 to 28 days prior to Period 2 (baseline; Week 0 [Visit 2]).
- **Period 2: Induction Dosing Period** will occur from Week 0 (baseline; Visit 2) to Week 12 (Visit 9), inclusive.
- **Period 3: Extension Period** will occur from Week 12 (Visit 9) up to Week 24 (Visit 12), inclusive.
- **Period 4: Post-Treatment Follow-Up Period** occurring from last treatment period visit (Week 24) or Early Termination Visit (ETV), for a minimum of 12 weeks following that visit.

In the remainder of this statistical analysis plan (SAP), if Period 2 (Induction Dosing Period) and Period 3 (Extension Period) are combined for analysis, they will be referred to as **Blinded Treatment Periods**.

Figure RHCR.5.1 illustrates the study design.

In addition to procedures specified in the protocol, a subset of patients will participate in a Photograph and/or Skin Biopsy addendum/addenda. Sites will be selected by the Sponsor, and some patients at those sites will participate in the addendum/addenda; separate informed consent(s) will be obtained.

Abbreviations: d = day(s); GUS = guselkumab; IXE = ixekizumab; LV = last visit; Q2W = every 2 weeks; Q4W = every 4 weeks; Q8W = every 8 weeks; R = randomization; V = study visit; W = study week.

Figure RHCR.5.1. Illustration of study design for Clinical Protocol I1F-MC-RHCR.

5.2. Method of Assignment to Treatment

At Week 0 (Visit 2), patients who meet all criteria for enrollment at Visits 1 and 2 will be randomized at a 1:1 ratio to double-blind treatment groups (i.e., ixekizumab or guselkumab) as determined by a computer-generated random sequence using an interactive web-response system (IWRS). The IWRS will be used to assign double-blind investigational product to each patient. The Unblinded Site Personnel at the site will confirm that they have located the correct assigned study drug package by entering a confirmation number found on the package into the IWRS.

Randomization will be stratified by site for this study.

5.3. Determination of Sample Size

Approximately 960 patients will be randomized at a 1:1 ratio to ixekizumab and guselkumab. With 480 patients per treatment group, this study will have 98% power to test the superiority of ixekizumab to guselkumab for a 100% reduction in the Psoriasis Area and Severity Index (PASI 100) at Week 12. The following assumptions were used for the power calculation response rate at Week 12: 35.3% and 23.0% for the ixekizumab and guselkumab groups, respectively. A 2-sided Fisher's exact test at a significance level of 0.05 is assumed. This study is also powered at 95% to test the superiority of ixekizumab for PASI 100 at Week 24, assuming the response rate of ixekizumab and guselkumab at 56% and 44%, respectively. These assumptions are based on the ixekizumab and guselkumab clinical studies in psoriasis (Griffiths et al. 2015; Gordon et al. 2016; Blauvelt et al. 2017; Reich et al. 2017).

For the non-inferior test of PASI 100 at Week 24, a non-inferiority margin of -11.4% is considered sufficiently small to be clinically unimportant difference in outcome between guselkumab and ixekizumab. This non-inferior margin is based on a 70% retention rate approach assuming a placebo response rate of 6.0% at Week 24 observed in a phase 2 study (Deodhar et al. 2018). The sample size of 480 patient per treatment group provides >99% power to test the non-inferiority.

6. A Priori Statistical Methods

6.1. General Considerations

Statistical analysis of this study will be the responsibility of Eli Lilly and Company (hereafter, Lilly). The statistical analyses will be performed using SAS® Version 9.2 or higher.

Not all displays described in this SAP will necessarily be included in the clinical study report (CSR). Any display described in this SAP and not provided in the CSR would be available upon request. Not all displays will necessarily be created as a “static” display. Some may be incorporated into interactive display tools instead of or in addition to a static display. Any display created interactively will be included in the CSR if deemed relevant to the discussion.

6.1.1. Analysis Populations

Unless otherwise specified, efficacy and health outcome analyses will be conducted on the intent-to-treat (ITT) population. Safety analyses for the Blinded Treatment Periods will be conducted on the safety population. Safety analyses for the Post-Treatment Follow-Up Period will be conducted on the post-treatment follow-up population. Analyses populations are defined in [Table RHCR.6.1](#).

Table RHCR.6.1. Definition of Analyses Populations

Population	Description
Intent-to-treat (ITT)	All randomized patients, even if the patient does not take the assigned treatment, does not receive the correct treatment, or otherwise does not follow the protocol. Patients will be analyzed according to the treatment group to which they were assigned in Period 2.
Safety	All randomized patients who take at least 1 dose of study drug. Participants will be included in the treatment group to which they were randomized. Patients will be analyzed according to the treatment group to which they were assigned in Period 2.
Post-treatment follow-up	All randomized patients who take at least 1 dose of study treatment and have entered the Post-Treatment Follow-Up Period. Patients will be analyzed according to the treatment group to which they were assigned in Period 2.

[Table RHCR.6.2](#) describes treatment groups and the comparisons for each study period and the analysis population.

Table RHCR.6.2. Treatment Groups and Comparisons for Each Study Period and Analysis Population

Study Period	Analysis Population	Treatment	Abbreviation	Comparison
Blinded Treatment Periods	Intent-to-Treat Population; Safety Population	Ixekizumab; Guselkumab	IXE GUS	IXE vs. GUS
Post-Treatment Follow-Up Period ^a	Post-treatment Follow-Up Population	Ixekizumab; Guselkumab	IXE GUS	No comparison

Abbreviations: GUS = guselkumab; IXE = ixekizumab; vs. = versus.

^a Treatment group refers to the treatment that the patients were assigned in Period 2.

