
 
• Skin Pain VAS                             
 
○ Skin Pain VAS (0)
 
○ Change from baseline
 
 
 
	
 
○ The proportion of patients achieving Skin Pain VAS (0) at Weeks 4, 8, 12, and 24 (restricted to those patients with Skin Pain VAS score >0 at baseline)
 
○ Change from baseline in Skin Pain VAS score at Weeks 4, 8, 12, and 24
 

 
• DLQI (0,1)
 
	
 
• The proportion of patients achieving DLQI (0,1) at Weeks 2, 4, 8, 12, and 24 (restricted to those patients with DLQI score >1 at baseline)
 

[figure not shown]
Abbreviations: DLQI = Dermatology Life Quality Index; NRS = Numeric Rating Scale; PASI = Psoriasis Area and Severity Index; Ps = plaque psoriasis; sPGA = static Physician Global Assessment; VAS = visual analog scale.

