## **7.2. Method of Treatment Assignment**

At Week 0 (Visit 2), patients who meet all criteria for enrollment at Visits 1 and 2 will be randomized at a 1:1 ratio to double-blind treatment groups (i.e., 80 mg ixekizumab or 100 mg guselkumab) as determined by a computer-generated random sequence using an interactive web-response system (IWRS). The IWRS will be used to assign blinded study drug to each patient. The Unblinded Site Personnel at the site will confirm that they have located the correct assigned study drug package by entering a confirmation number found on the package into the IWRS as described for Unblinded Site Personnel in the Unblinded Site Personnel Dispensing and Dosing Instructions.

Randomization will be stratified by site for this study.

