### 10.2. Populations for Analyses

Unless otherwise specified, efficacy and health outcome analyses will be conducted on the intent-to-treat (ITT) population; whereas, safety analyses will be conducted on the safety population defined below:

Population	Description
Intent-to-Treat Population	All randomized patients, even if the patient does not take the assigned treatment, does not receive the correct treatment, or otherwise does not follow the protocol. Patients will be analyzed according to the treatment to which they were assigned.
Safety	All randomized participants who take at least 1 dose of study drug. Participants will be included in the treatment group to which they were randomized. In the event of a treatment error, participants will be analyzed according to the treatment they actually received.

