The primary analyses for the continuous efficacy and health outcome variables will be performed using mixed effects model for repeated measures (MMRM) analysis. The model will include treatment, pooled site, baseline value, visit, treatment-by-visit interaction and baseline value-by-visit as fixed factors. A secondary analysis for continuous efficacy and health outcomes variables will be made using analysis of covariance (ANCOVA) adjusting for pooled site and baseline value.

Fisher's exact test will be used for all AE, baseline, discontinuation, and other categorical safety data. Continuous laboratory values will be analyzed by an ANCOVA with treatment and baseline value in the model.

Any change to the data analysis methods described in the protocol will require an amendment ONLY if it changes a principal feature of the protocol. Any other change to the data analysis methods described in the protocol, and the justification for making the change, will be described in the clinical study report (CSR). Additional exploratory analyses of the data will be conducted as deemed appropriate.

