6.14. Safety Analyses

Safety will be assessed by summarizing and analyzing AEs, laboratory analyses, vital signs, and Columbia-Suicide Severity Rating (C-SSRS). The duration of treatment exposure will also be summarized.

The primary safety analyses will focus on the comparison of ixekizumab to guselkumab for the Blinded Treatment Periods. For the Post-Treatment Follow-Up Period, safety data will be summarized according to the treatment which patients had received in the Blinded Treatment Periods.

All safety analyses will be conducted on the Safety Population.

Comparisons between treatment groups will be conducted using Fisher's exact test

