6.14.1. Extent of Exposure

Duration of exposure to study drug will be summarized by treatment for safety population during the Blinded Treatment Periods using descriptive statistics.

The duration of exposure to treatment during the Blinded Treatment Periods will be calculated as:

Duration of exposure (days) =

Date of last visit (scheduled or unscheduled) in the Blinded Treatment Periods – Date of first injection + 1

For patients who discontinued treatment due to lost to follow-up, duration of exposure will be calculated with date of second to the last visit (scheduled or unscheduled) in treatment period will be used in replacement of date of last visit (scheduled or unscheduled) in treatment period.

The number and percentage of patients in each of the following categories will be included in the summaries:

- >0, ≥7 days, ≥14 days, ≥30 days, ≥60 days, ≥90 days, ≥120 days, and ≥168 days.
Note that patients may be included in more than 1 category.
- >0 to <7 days, ≥7 to <14 days, ≥14 to <30 days, ≥30 to <60 days, ≥60 days to <90 days, ≥90 to <120 days, ≥120 to <168 days, and ≥168.

The summaries will also include the following information:

- Total exposure in patient years, calculated as:

Total exposure in patient years =

Sum of duration of exposures with the defined treatment period (for all patients in treatment group) / 365.25

- Number of active injections taken is derived using the response to the question “Was dose administered?” on the Exposure eCRF page and the actual dose description from IWRS study drug dispense dataset.
- Total dose (in mg) is calculated as:

Total Dose = Sum of dose for each active injection taken during the defined treatment period

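### Two SAP rules depart from the protocol without a stated reason: safety follows the assigned arm even after a treatment error, and the exploratory DLQI (0,1) endpoint loses its baseline >1 restriction

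*SAP*

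**What the plan says.** **Safety grouping.** Protocol 10.2 groups safety patients by randomized arm and then adds: "In the event of a treatment error, participants will be analyzed according to the treatment they actually received". The safety row of SAP Table RHCR.6.1 keeps the grouping sentence, but the exception is gone. In its place stands the sentence that closes the SAP's ITT row, so patients fall in the group "to which they were randomized. Patients will be analyzed according to the treatment group to which they were assigned in Period 2". Footnote a of SAP Table RHCR.6.2 applies the same rule to follow-up: "Treatment group refers to the treatment that the patients were assigned in Period 2". SAP 6.14 words the follow-up period differently: "safety data will be summarized according to the treatment which patients had received in the Blinded Treatment Periods".

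**DLQI (0,1).** The protocol endpoint in Table RHCR.4.1 is "The proportion of patients achieving DLQI (0,1) at Weeks 2, 4, 8, 12, and 24 (restricted to those patients with DLQI score" above 1 at baseline). SAP Table RHCR.4.1 lists the same endpoint and weeks with no restriction. SAP Table RHCR.6.7 gives its population simply as ITT, and SAP Table RHCR.6.6 derives the response from the post-baseline total alone.

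**Changes of method.** Protocol 10.3.1 requires an amendment only when a principal feature changes. Other changes are to be described and justified in the clinical study report.

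**The concern.** Each SAP rule, followed as written, produces a table that differs from what the protocol promises.

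For safety, a patient given the other arm's drug stays in the assigned column, so an adverse event that follows the wrong drug is counted against the drug the patient should have had.

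For DLQI (0,1), a patient who enters at 0 or 1 and stays there counts as a responder without having improved. The entry criteria set no DLQI minimum, so such patients can be enrolled. They raise both response rates if they respond more often than the others, and they dilute the treatment difference if they respond equally in both arms.

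Nothing confirmatory is at stake. DLQI (0,1) is exploratory with no multiplicity control, and neither rule touches the primary or major secondary tests.

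**Working it through.** The plan gives no figure on this point to reproduce. The check sets the texts side by side and then illustrates the size.

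**1. Safety rule.**

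| Source | Group used after a treatment error |
|---|---|
| Protocol 10.2 | Treatment actually received |
| SAP Table RHCR.6.1, safety and follow-up rows | Group assigned in Period 2 |
| SAP Table RHCR.6.2, footnote a | Group assigned in Period 2 |
| SAP 6.14, follow-up | Treatment received |

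The SAP does not mention treatment errors. That safety stays with the assigned arm follows from its unqualified rule and the missing exception. Other SAP displays use exposure: 6.14.1 counts active injections from "the actual dose description from IWRS study drug dispense dataset", and the eDISH plot in Table RHCR.6.8 splits patients by whether they ever received ixekizumab.

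**2. Baseline restrictions on the exploratory responder endpoints.**

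| Endpoint | Protocol Table RHCR.4.1 | SAP Tables RHCR.4.1 and RHCR.6.7 |
|---|---|---|
| Itch NRS responder | ≥4 | ≥4 |
| Itch NRS (0) | >0 | >0 |
| Skin Pain VAS (0) | >0 | >0 |
| DLQI (0,1) | >1 | none |

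This is not a general move to all ITT patients: SAP Table RHCR.6.7 limits the DLQI improvement of at least 5 points to patients with baseline ≥5. SAP Table RHCR.6.3 splits baseline DLQI only at 5 and at 11, so the tabulated summary does not show how many patients start at 0 or 1.

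**3. Size, safety.** With no treatment error the two rules agree. As a constructed case, take 480 per arm (the planned number) and a rare event in 2 patients per arm as assigned. One patient with the event, assigned to one arm, received the other arm's drug.

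- As assigned: 2/480 − 2/480 = 0
- As received: 3/481 − 1/479 = 0.62% − 0.21% = 0.41 points

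**4. Size, DLQI (0,1).** Let f be the share of each arm with baseline DLQI 0 or 1, s their response rate (equal in both arms), and pI, pG the rates in the other patients.

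- Reported rate = f·s + (1 − f)·p
- Reported difference = (1 − f)·(pI − pG)

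The documents give none of these. Assumed: f = 2%, 5%, 10%; pI = 65%, pG = 55%; s = 95%. The last takes the 5% dropout in Protocol 5.2 as nonresponse and further assumes that everyone who remains stays at 0 or 1. For f = 5%: 0.05 × 0.95 + 0.95 × 0.65 = 66.5%, and 0.05 × 0.95 + 0.95 × 0.55 = 57.0%.

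The z value is unstratified: difference / √{[pI(1 − pI) + pG(1 − pG)]/n}. For the all-ITT column, the reported rates are used with n = 480.

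| f | Patients per arm at 0–1 | All-ITT rates | Difference | z, all ITT (n = 480) | z, restricted (n) |
|---|---|---|---|---|---|
| 2% | about 10 | 65.6% vs 55.8% | 9.8 | 3.12 | 3.15 (470) |
| 5% | 24 | 66.5% vs 57.0% | 9.5 | 3.04 | 3.10 (456) |
| 10% | 48 | 68.0% vs 59.0% | 9.0 | 2.91 | 3.02 (432) |

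The restricted difference is 10.0 points throughout. The difference column depends on s being equal in the two arms, not on its value.

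**The case against.** The strongest reply is that little turns on this and that the protocol leaves room for it.

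- **Permission.** Protocol 10.3.1 lets a non-principal change be justified in the study report, and 10.3.3.3 leaves the details of exploratory analyses to the SAP. So the missing reason is not in itself a breach. That stands. But removing a baseline restriction changes who is in the endpoint, which is more than an analysis detail.
- **Size and direction.** If response among the already-0–1 patients is equal in both arms, the unrestricted analysis shrinks the difference, which works against a superiority claim. Entry requires PASI ≥12, sPGA ≥3 and BSA ≥10% at screening and baseline, so f may be small. SAP Table RHCR.6.7 also analyses DLQI change and DLQI improvement. All of this limits the consequence, but the reported rates would still not be the protocol's.
- **Visibility.** SAP 6.7.1 plans by-patient baseline listings, so patients at 0 or 1 could be counted by hand. That is correct; the gap is in the tabulated categories only.
- **Treatment errors.** Package confirmation through the IWRS makes them unlikely: "The Unblinded Site Personnel at the site will confirm that they have located the correct assigned study drug package". Dosing takes place at nine visits, so a single wrong syringe would leave a patient exposed to both drugs, and Protocol 10.2 does not say how to classify mixed exposure. This stands: the protocol rule alone does not settle that case, hence the listing proposed below.
- **Wording of SAP 6.14.** Its reference to treatment received may only mean the study arm, and no between-arm comparison is planned in follow-up. That reading is possible, and it is a reason to align the wording.

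**Conclusion.** Both departures are in the text, and neither document gives a reason. The impact is minor. The safety rule has no effect without a treatment error; the 0.41-point shift is an illustration, not a forecast. For DLQI (0,1), the 10.0-point difference falls to between 9.8 and 9.0 points under assumed f of 2% to 10% and equal response among the already-0–1 patients. No conclusion changes in that range. The case for correction is that the report should show the endpoint and the safety grouping the protocol defines, or explain why it does not. These two are not a complete list of SAP differences from the protocol.

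**What to change.** Preferably before the Week 12 database lock, when part of the sponsor's team is unblinded:

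1. In the safety and follow-up rows of SAP Table RHCR.6.1 and the Table RHCR.6.2 footnote, restore analysis by treatment actually received after a treatment error, and align 6.14.
2. List every patient who received both drugs, with event onset and the drug given before it. The Exposure eCRF and the dose description used in 6.14.1 supply this.
3. In SAP Tables RHCR.4.1 and RHCR.6.7, restrict DLQI (0,1) to ITT patients with baseline DLQI >1 and keep the all-ITT version as supportive.
4. Add a ≤1/>1 baseline DLQI category to SAP Table RHCR.6.3.
5. If either departure is intended, state the reason.

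Optionally, use the same DLQI denominator in the exploratory AUC analysis in SAP 6.11.3. The protocol has no AUC endpoint, so this is for consistency only.

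The cost is SAP wording, one denominator filter, one baseline category and one listing, all from data already collected. The DLQI (0,1) denominator falls to about 470, 456 or 432 per arm at f = 2%, 5% or 10%. Under the assumed rates this costs no power, since the restricted z is slightly higher each time.

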6.1.2. Baseline Definition

For the Blinded Treatment Periods, the baseline value will be defined as the last available value before the first treatment injection for both efficacy/health outcomes and safety analyses. In most cases, this will be the measure recorded at Week 0 (Visit 2). For efficacy/health outcome measures, if the patient does not take any injection, the last available value on or prior to randomization date will be used.

Change from baseline will be calculated as the postbaseline value minus the baseline value. Percent change from baseline is defined as: 100 times the change from baseline divided by baseline). Percent improvement from baseline is calculated as: the positive percent change from baseline if a higher value postbaseline means improvement from baseline; and as the negative percent change from baseline if a lower value postbaseline means improvement from baseline. If the baseline value is missing for a particular variable, then the change from baseline and the percent improvement from baseline will not be calculated.

For safety analyses using a baseline period, the baseline period is defined as the time from Visit 1 to the date/time of the first injection.

For the Post-Treatment Follow-Up Period, the baseline is defined as the last nonmissing assessment on or prior to entering Period 4, that is, on or prior to Week 24 (Visit 12), or at the early termination visit (ETV).

6.1.3. Analysis Methods

The randomization to treatment groups is stratified by site, as described in Section 5.2. For statistical purposes, study sites with fewer than 5 randomized patients per treatment group will be pooled from smallest to largest (in terms of total number of patients per site and site identification number), until the pooled site had 5 or more patients per treatment group. If there are still sites with fewer than 5 patients per treatment group remaining after the pooling, those sites will be included in a pooled site with the smallest number of patients in total. Each pooled site will be considered as a single site for all efficacy and health outcome analyses.

The primary analysis method for treatment comparisons of categorical efficacy and health outcomes variables will be made using a Cochran-Mantel-Haenszel (CMH) test stratified by pooled site. Missing data will be imputed using the nonresponder imputation (NRI) method. The treatment response rates and their corresponding 95% confidence intervals (CIs), using normal approximation, as well as the treatment differences, will be reported. Secondary analysis will be conducted using a Fisher's exact test.

The primary analyses for the continuous efficacy and health outcome variables will be performed using mixed effects model for repeated measures (MMRM) analysis. The model will include treatment, pooled site, baseline value, visit, treatment-by-visit interaction, and baseline value-by-visit as fixed factors. A secondary analysis for continuous efficacy and health outcomes variables at specific time point will be made using analysis of covariance (ANCOVA) adjusting for pooled site and baseline value.

When the MMRM model is used, the covariance structure to model the within-patient errors will be unstructured. The restricted maximum likelihood (REML) will be used. The Kenward-Roger method will be used to estimate the denominator degrees of freedom. The Newton-Raphson with ridging optimization technique will be used to aid with convergence. If the unstructured covariance matrix results in a lack of convergence, the heterogeneous Toeplitz covariance structure, followed by the heterogeneous autoregressive covariance structure, followed by the compound symmetric structure will be used. The first structure to yield convergence will be used for inference. Type III tests for the least squares (LS) means will be used for the statistical comparisons; the corresponding 95% CIs will also be reported.

When the ANCOVA model is used, missing data will be imputed using the modified baseline observation carried forward (mBOCF). Type III sums of squares for the LS means will be used for the statistical comparisons; the 95% CI will be reported.

The Kaplan-Meier product limit method will be used to estimate the survival curves for time-to-event variables. Treatment comparisons will be performed using the log-rank test. Patients completing the Blinded Treatment Periods without event will be censored at the date of completion (that is, the date of the last visit in the Blinded Treatment Periods). Patients without a date of completion or discontinuation for the Blinded Treatment Periods will be censored at the latest non-missing date out of the following dates: date of last dose and date of last attended visit in the Blinded Treatment Periods.

Fisher's exact test will be used for all adverse event (AE), categorical baseline characteristics, discontinuation, and other categorical safety data. The continuous baseline characteristics will be analyzed using an analysis of variance (ANOVA) model with treatment as a factor. Continuous vital sign data and laboratory values will be analyzed by an ANCOVA with treatment and baseline value in the model. For condition/event that is gender-specific (as defined by the Medical Dictionary for Regulatory Activities [MedDRA]), the denominator and computation of the percentage will include only patients from the given gender.

Data collected at ETVs will be mapped to the next planned visit number for that patient. For by-visit summaries, only visits in which a measure was scheduled to be collected will be

summarized. Unplanned/Unscheduled measurements will be excluded from the MMRM analysis. However, the data will still be used in other analyses; such analyses include, but are not limited to, shift analyses and mBOCF endpoint analyses.

All CIs and statistical tests will be 2-sided with an alpha-level of 0.05, unless specified otherwise.

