6.2. Adjustments for Covariates

Randomization at the beginning of Period 2 is stratified by site. Unless otherwise specified, all efficacy and health outcome analyses during the Blinded Treatment Periods will include pooled site in the model.

In general, when an MMRM is used for analyses, treatment, pooled site, baseline value, visit, treatment-by-visit interaction, and baseline value-by-visit are included as covariates; when an ANCOVA is used for analyses, treatment, pooled site and baseline value will be included as covariates.

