PGA-F	PGA-F (0, 1) with at least a 2-point improvement from baseline; PGA-F (0) with at least a 2-point improvement from baseline	CMH test with NRI; Fisher’s Exact test with NRI	ITT Population – Patients with baseline PGA-F ≥3	IXE vs. GUS at all postbaseline visits	Exploratory analysis (Section 6.11.3).

Abbreviations: ANCOVA = Analysis of Covariance; BSA = Percentage of Body Surface Area; CMH = Cochran-Mantel-Haenszel; GUS = guselkumab 100 mg; ITT = Intent-to-Treat; IXE = ixekizumab 80 mg; mBOCF = modified baseline observation carried forward; MMRM = Mixed-effects Model of Repeated Measures; NRI = Nonresponder Imputation; PASI = Psoriasis Area and Severity Index; PASI 50/75/90/100 = at least a 50%/75%/90%/100% improvement from baseline in PASI score; PGA-F = Physician’s Global Assessment of Fingernail Psoriasis; sPGA=static Physician Global Assessment; VAS = Visual Analogue Scale; vs. = versus.

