	Itch NRS ≥ 4 improvement from baseline	CMH test with NRI; Fisher’s Exact test with NRI	ITT Population - with baseline Itch NRS Score ≥ 4	IXE vs. GUS at all post-baseline visits	Exploratory analysis (Section 6.11.3).
	Itch NRS = 0	CMH test with NRI; Fisher’s Exact test with NRI	ITT Population - with Baseline Itch NRS Score > 0	IXE vs. GUS at all post-baseline visits	Exploratory analysis (Section 6.11.3).
DLQI	DLQI total score and domain scores change from baseline	MMRM; ANCOVA with mBOCF for the Blinded Treatment Periods	ITT Population	IXE vs. GUS at all post-baseline visits	Exploratory analysis (Section 6.11.3).
	DLQI ≥ 5 improvement from baseline	CMH test with NRI; Fisher’s Exact test with NRI	ITT Population with Baseline DLQI ≥ 5	IXE vs. GUS at all post-baseline visits	Exploratory analysis (Section 6.11.3).
	DLQI (0, 1)	CMH test with NRI; Fisher’s Exact test with NRI	ITT Population	IXE vs. GUS at all post-baseline visits	Exploratory analysis (Section 6.11.3).
Skin Pain VAS	Skin Pain VAS change from baseline	MMRM; ANCOVA with mBOCF for the Blinded Treatment Periods	ITT Population	IXE vs. GUS at all post-baseline visits	Exploratory analysis (Section 6.11.3).
	Skin Pain VAS = 0	CMH test with NRI; Fisher’s Exact test with NRI	ITT Population – with baseline Skin Pain VAS > 0	IXE vs. GUS at all post-baseline visits	Exploratory analysis (Section 6.11.3).
Patient’s Global Assessment of Disease Severity (PatGA)	PatGA (0)	CMH test with NRI; Fisher’s Exact test with NRI	ITT Population	IXE vs. GUS at all post-baseline visits	Exploratory analysis (Section 6.11.3).
	PatGA (0, 1)	CMH test with NRI; Fisher’s Exact test with NRI	ITT Population	IXE vs. GUS at all post-baseline visits	Exploratory analysis (Section 6.11.3).
	PatGA ≥ 2 improvement from baseline	CMH test with NRI; Fisher’s Exact test with NRI	ITT Population with Baseline PatGA ≥ 2	IXE vs. GUS at all post-baseline visits	Exploratory analysis (Section 6.11.3).

Measure	Variable	Analysis Method (Sections 6.1.3 and 6.3)	Analysis Population (Section 6.1.1)	Comparison / Time Point	Analysis Type
Patient's Assessment of Pain VAS	Patient's Pain VAS change from baseline; percent improvement	ANCOVA with mBOCF; MMRM for the Blinded Treatment Periods	ITT Population – with psoriatic arthritis at baseline	IXE vs. GUS at all post-baseline visits	Exploratory analysis (Section 6.11.3).

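### Pooled sites sized on all randomized patients are reused in the psoriatic arthritis and PGA-F ≥3 analyses, which may cost precision in these exploratory comparisons

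*SAP*

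**What the plan says.** SAP 5.2 stratifies randomization by site and by nothing else. SAP 6.1.3 pools sites with fewer than 5 randomized patients per arm, from smallest to largest, until that floor is reached, and then states: "Each pooled site will be considered as a single site for all efficacy and health outcome analyses". SAP 6.2 makes this the default: unless otherwise specified, "all efficacy and health outcome analyses during the Blinded Treatment Periods will include pooled site in the model".

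Two groups of exploratory analyses use only part of the ITT population:

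- **Nail psoriasis.** Table RHCR 6.5 analyses two PGA-F responses in "ITT Population – Patients with baseline PGA-F ≥3", by CMH with NRI and by Fisher's exact test with NRI.
- **Joint measures.** The physician's global VAS (Table RHCR 6.5) is limited to patients with psoriatic arthritis at baseline. So are the patient's pain VAS and the patient's global VAS (Table RHCR.6.7: "ITT Population – with psoriatic arthritis at baseline"). All three are analysed by ANCOVA with mBOCF and by MMRM.

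No text pools again, or drops site, for these sets. SAP 6.17.1 withholds inferential testing when a subgroup category is under 10% of ITT. That rule covers only the subgroup analyses, whose logistic and Fisher methods do not use site.

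**The concern.** The 5-per-arm floor exists so that every stratum can compare the two arms. It is counted on all randomized patients, so it gives no such assurance inside a subset. A pooled site with 5 patients per arm holds on average one subset patient if the subset is 10% of the trial.

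A stratum with one arm only adds zero to the CMH statistic and almost nothing to a treatment contrast with site as a fixed factor. What is at stake is precision: a null nail or joint result could partly reflect how the strata were defined. If the strata were changed only after unblinding, the change would be data-dependent.

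**Working it through.** **Inputs from the documents.** "Approximately 960 patients will be randomized at a 1:1 ratio to ixekizumab and guselkumab" (SAP 5.3), so 480 per arm; randomization stratified by site only (SAP 5.2); a pooling floor of 5 randomized patients per arm (SAP 6.1.3).

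**Assumed, because the documents do not give them.** Subset prevalence q; 40 to 160 sites; unequal site sizes (gamma, shape 1.5); randomization blocks of 4; no site effect on outcome.

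**Step 1. The plan's own figure.** SAP 5.3 says "this study will have 98% power to test the superiority of ixekizumab to guselkumab", at "35.3% and 23.0% for the ixekizumab and guselkumab groups, respectively", and "A 2-sided Fisher's exact test at a significance level of 0.05 is assumed". Exact enumeration with 480 per arm gives 98.6%. For Week 24 (56% vs 44%) it gives 95.5% against a stated 95%. Both agree. These are full-ITT figures; the plan claims no power for the subsets.

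**Step 2. Measure of information.** With m1 and m2 subset patients per arm in a stratum, and M1 and M2 in the whole subset:

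share kept = Σ[m1·m2/(m1+m2)] ÷ [M1·M2/(M1+M2)]

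This is the null-variance weight of the CMH test. It holds approximately for ANCOVA or MMRM with site as a fixed effect.

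**Step 3. Smallest permitted stratum, 5 per arm, q = 10%.** The chance that an arm has no subset patient is 0.9^5 = 0.590.

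- One arm only: 2 × 0.590 × 0.410 = 48% of strata.
- Empty: 0.590² = 35%.
- Both arms: 0.410² = 17%.

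Applying the formula with m1 and m2 each binomial(5, 0.10) gives 39% kept, so 61% lost. At q = 20% and 30% the losses are 38% and 25%. With 10 per arm they are 41%, 21% and 12% at q = 10%, 20% and 30%.

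**Step 4. Mixed site sizes.** The SAP 6.1.3 pooling rule was applied to 960 simulated patients (400 runs per setting). With 40 to 160 sites it yields 33 to 67 pooled sites. Ranges run from 40 to 160 sites:

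| Subset share q | Strata with one arm only | Information lost as written | Information kept after pooling within the subset |
|---|---|---|---|
| 10% | 36-49% | 28-51% | about 95-96% |
| 20% | 17-34% | 14-29% | about 95-96% |
| 30% | 7-16% | 8-18% | about 96-97% |

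At q = 60% the loss is about 3-6%, and at 90% about 1-2%.

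**Step 5. What this means for power.** Take a subset comparison that would have 80% power without stratification. With share f kept, power is Φ[(1.960 + 0.842)·√f − 1.960].

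- q = 10% (f = 0.49 to 0.72): 50% to 66%.
- q = 20% (f = 0.71 to 0.86): 66% to 74%.
- q = 30% (f = 0.82 to 0.92): 72% to 77%.
- After pooling within the subset (f about 0.96): 78%.

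**The case against.** The strongest reply is that the size is unknown and the stakes are low. Much of it stands.

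- **Size.** Site numbers and prevalences are not in the documents. A reader might infer that most strata will hold one arm and that a large share of the information is certain to go. The documents do not support that as fact. It depends on a subset near 10% or smaller, or up to about 20% with most pooled sites near the floor. Only sites below the floor are merged, so larger sites keep their size and the loss is smaller than Step 3 suggests.
- **Discarded patients.** A reader might infer that the plan throws away enrolled patients. For PGA-F it does not: the secondary Fisher's exact test is unstratified and uses every subset patient. Only the CMH test is affected. The VAS measures have no site-free counterpart.
- **Number of site parameters.** The rule allows at most 960/10 = 96 pooled sites, so a reader might infer about 95 site parameters in a small subset. An empty site uses none. Even with 96 minimum-size sites, 96 × (1 − 0.9^10) ≈ 63 are occupied at q = 10%. In the mixed-size simulation, occupied sites run from about 33 × 0.88 ≈ 29 (40 sites, q = 10%) to 67 × 0.94 ≈ 63 (160 sites, q = 20%).
- **Status.** The affected analyses are exploratory, unadjusted for multiplicity and unpowered. No bias or type I error inflation has been shown.

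None of this removes the gap: a floor chosen to keep both arms in each stratum is not kept in these sets, and nothing in the SAP handles it.

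**Conclusion.** The point holds as a minor one. The strata are built once on all randomized patients and carried unchanged into the psoriatic arthritis VAS models and the PGA-F ≥3 CMH test. The likely cost is roughly 15-50% of the information on the treatment contrast if a subset is 10-20% of patients, and about 8-18% at 30%.

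These figures rest on the assumed 40 to 160 sites, the assumed spread of site sizes and the assumed prevalences. They also assume no site effect; a real one would offset part of the loss, since adjustment would then remove some variance. The gap matters most for the three VAS measures, where both planned models include site. The full-ITT primary and major secondary tests are not affected.

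**What to change.** Add to SAP 6.1.3, before unblinding: for the analyses restricted to patients with psoriatic arthritis at baseline and to patients with baseline PGA-F ≥3, the same pooling algorithm is re-applied to the patients in that analysis set, so that each pooled site has at least 5 patients per treatment group in that set.

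Leave the strata unchanged for the full-ITT analyses and for the PASI ≥12 and sPGA ≥3 sets. Those two thresholds are entry criteria (Protocol 6.1), so these sets are nearly the whole ITT population and re-pooling would gain almost nothing.

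The cost is one sentence and another run of the pooling step. Site strata will differ between full-ITT and subset tables, which a footnote can state. Omitting site in the two subsets would also work and avoids the loss altogether, but it departs from the SAP 6.2 default of adjusting for the stratification factor.
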